4.1.1. Part 1: Dose-Escalation Phase

Cohort Size: The initial dose cohort(s) will include up to three participants per GSK3368715 dose level. Cohorts will be expanded at the first instance of a \geq Grade 2 drug-related non-hematological toxicity. From there on, a minimum of 3 and a maximum of 12 DLT evaluable participants may be assigned to any single dose at the discretion of the Dose Escalation Committee (DEC) as outlined in the Dose Escalation Plan.

Replacement: If a participant fails to receive at least 75% of the planned doses within the 21-day DLT observation period for reasons other than toxicity (e.g., concurrent illness or disease progression), the participant will be replaced by additional participant(s) assigned to the same dose level and will not be counted as DLT evaluable.

Dose Escalation: After each dose cohort, a dosing recommendation for the next cohort will be made using the Neuenschwander Continual Reassessment Method (N-CRM) [[Neuenschwander, 2008](#)].

The N-CRM design makes use of a Bayesian logistic regression model relating dose and toxicity and is expected to locate the target dose level efficiently while minimizing the number of participants exposed to pharmacologically inactive or unsafe dose levels. The N-CRM method is fully adaptive and makes use of all DLT information, therefore is expected to locate the target dose level efficiently.

The N-CRM estimates, for each potential dose, the posterior probabilities that the DLT rate lies in each of four toxicity ranges:

- A dose falls in the **Under-dosing** range if the probability of a DLT at the dose is, 16%.
- A dose falls in the **Target** Toxicity range if the probability of a DLT at the dose is $\geq 16\%$ and $< 33\%$.
- A dose falls in the **Excessive** Toxicity range if the probability of a DLT at the dose is $\geq 33\%$, and $< 60\%$.
- A dose falls in the **Unacceptable** Toxicity range if the probability of a DLT at the dose is $\geq 60\%$

At the time of each dose-escalation decision, the dose with the highest posterior probability of lying in the Target Toxicity range will be the model-recommended dose for

the next cohort. Additionally, the following constraints for the recommended dose will be maintained:

- The posterior probability of the DLT rate lying in the Excessive Toxicity or Unacceptable Toxicity range is less than 25%.
- VTE safety rules

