9.6.2. Safety Analyses

The All-Treated Population will be used for the analysis of safety data.

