9.6.2.2. Adverse Events

AEs will be coded using the standard MedDRA and grouped by system organ class. AEs will be graded by the investigator according to the NCI-CTCAE v5.

Events will be summarized with frequency and percentage by preferred term. Separate summaries will be provided for all AEs regardless of grade, intervention-related AEs, intervention-related AEs by maximum grade, serious adverse events (SAEs), intervention-related SAEs, AEs leading to discontinuation of study intervention, AEs leading to dose reductions and AEs leading to dose interruptions/delays. Details will be provided in the RAP.

DLTs will be listed and summarized by dose cohort for Part 1.

The incidence of deaths and the primary cause of death will be summarized.

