## 4. ANALYSIS POPULATIONS

| Population           | Definition / Criteria  | Analyses Evaluated   |
|----------------------|--|--|
| Screened             | 
 
All participants who were screened for eligibility
 
   | 
 
Study Population
 
   |
| Evaluable            | 
 
All participants who have had Week 24 disease assessments, have progressed or died, or permanently discontinued from the study intervention.
 
 |  |
| All-Treated          | 
 
All participants who received at least one dose of GSK3368715.
 
   | 
 
Study Population
 
Final Efficacy
 
Safety
 
 |
| Pharmacokinetic (PK) | 
 
Participants in the All-Treated population from whom at least one PK sample was obtained, analysed, and was measurable.
 
                      | 
 
PK
 
   |

Refer to [Appendix 10](#): List of Data Displays which details the population used for each display.

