## 8. SAFETY ANALYSES

The safety analyses will be based on the All-Treated population, unless otherwise specified.

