| 3.17.                               | All Treated       | EG2                             | Summary of Change from Baseline in ECG Values by Visit                        | IDSL                     | SAC                |
| Vital Signs                  |                   |                                 |   |                          |                    |
| 3.18.                               | All Treated       | VS1                             | Summary of Change from Baseline in Vital Signs                                | ICH E3                   | SAC                |
| Dose Modifications           |                   |                                 |   |                          |                    |
| 3.19.                               | All Treated       | ODMOD1                          | Summary of Dose Reductions of GSK3368715                                      | ICH E3                   | SAC                |
| 3.20.                               | All Treated       | ODMOD2                          | Summary of Dose Interruptions of GSK3368715                                   | ICH E3                   | SAC                |
| 3.21.                               | All Treated       | ODMOD8                          | Summary of Dose Escalations of GSK3368715                                     | If applicable.           | SAC                |
| Dose Limiting Toxicity (DLT) |                   |                                 |   |                          |                    |
| 3.22.                               | All Treated       | DL1                             | Summary of Dose-Limiting Toxicities during the Determinative Period           | ICH E3                   | SAC                |

| Safety: Tables            |             |                      |  |                   |             |
|---------------------------|-------------|----------------------|--|-------------------|-------------|
| No.                       | Population  | IDSL / Example Shell | Title  | Programming Notes | Deliverable |
| Performance Status |             |                      |  |                   |             |
| 3.23.                     | All Treated | PS1A                 | Summary of ECOG Performance Status                         | ICH E3            | SAC         |

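### SAP Table 3.22, the only summary table of the primary DLT endpoint, leaves non-evaluable participants in its denominator and does not say which of two DLT windows it covers

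*SAP*

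**What the plan says.** The display list in SAP 14.10.5 has one DLT summary, Table 3.22, titled "Summary of Dose-Limiting Toxicities during the Determinative Period". Its population is All Treated and it is due at the final analysis. Listing 22 (SAP 14.10.8) names the same period and is the only other DLT display. SAP 8.2 says DLTs are reported to the sponsor's oncology data standards, which are not supplied. It gives neither a denominator nor a window.

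**Population.** SAP section 4 defines All-Treated as "All participants who received at least one dose of GSK3368715". SAP section 8 states: "The safety analyses will be based on the All-Treated population, unless otherwise specified". This follows protocol 9.6.2 ("The All-Treated Population will be used for the analysis of safety data") and 9.6.2.2 ("DLTs will be listed and summarized by dose cohort for Part 1"). Neither protocol 9.3 nor SAP section 4 lists a DLT-evaluable set.

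**Evaluability.** Protocol 4.1.1 sizes dose levels in evaluable participants: "a minimum of 3 and a maximum of 12 DLT evaluable participants may be assigned to any single dose". Under its replacement rule, a participant who "fails to receive at least 75% of the planned doses within the 21-day DLT observation period for reasons other than toxicity" "will be replaced by additional participant(s) assigned to the same dose level and will not be counted as DLT evaluable".

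**Windows.** Protocol 4.1.3 and SAP 3.1 give 21 days for DLTs in general. Protocol 4.1.3 with Table 6, and SAP 2.3, give 8 (±1) weeks for a qualifying VTE (Grade 2 needing systemic anticoagulation, or Grade 3 and above), or less if the participant leaves the study sooner.

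**The concern.** The protocol builds its dose levels on evaluable participants, but its evaluability rule reaches no analysis of the endpoint it was written for. A replaced participant without a DLT and the replacement both count in the denominator of Table 3.22, which can only lower the percentage.

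The window matters because VTE is the toxicity that paused enrolment, and it is the one with the longer DLT window. A programmer who takes the period from SAP 3.1 would stop at Day 21. One who takes it from SAP 2.3 would carry qualifying VTEs to about week 8. The same data could then give two different primary-endpoint tables. The RP2D analysis is cancelled (SAP 2.1), so this table carries the final account of DLT incidence.

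**Working it through.** The plan gives no figure to reproduce, because it states no DLT counts and no number of non-evaluable participants. The check is a comparison of passages with simple arithmetic on assumed counts.

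**1. Denominator.** Let n be the evaluable participants at a dose level, m the DLT-free participants replaced under protocol 4.1.1, and x the DLTs, all in evaluable participants.

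- Rate per evaluable participant: x/n.
- Rate in Table 3.22: x/(n+m).
- Ratio of the second to the first: n/(n+m). It is below 1 whenever m is at least 1, and equals 1 when m = 0. If x = 0, both rates are zero.

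With m = 1 and n inside the protocol's range of 3 to 12 (x and m assumed):

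| n | x | x/n | x/(n+1) | ratio |
|---|---|---|---|---|
| 3 | 1 | 33.3% | 25.0% | 0.750 |
| 6 | 1 | 16.7% | 14.3% | 0.857 |
| 6 | 2 | 33.3% | 28.6% | 0.857 |
| 12 | 4 | 33.3% | 30.8% | 0.923 |

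**2. Window.** The term Determinative Period occurs only in the titles of Table 3.22 and Listing 22. SAP 14.4 defines study phases for concomitant medication only, and SAP 14.3 applies no assessment window.

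- VTE window in days: 7 × 7 = 49, 8 × 7 = 56, 9 × 7 = 63.
- Days after Day 21: 49 − 21 = 28, 56 − 21 = 35, 63 − 21 = 42.
- Share of the VTE window that a 21-day reading leaves out: 28/49 = 57.1%, 35/56 = 62.5%, 42/63 = 66.7%. These are shares of calendar days, not of events.
- First scheduled on-treatment imaging, which includes chest CT, is Week 9 Day 1: 8 × 7 + 1 = Day 57. With the ±7 days of protocol 8.1 it falls on Days 50 to 64. A VTE first seen on that scan is outside a 21-day period.

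**3. Who has the VTE window.** Protocol 2.2.1.4.3 counts 19 participants dosed at 50 to 200 mg by Amendment 3. Protocol 1.1 describes the VTE period as added under that amendment, and 4.1.1 ties the VTE criteria to re-initiation of enrolment. The bullet in protocol 4.1.3 that makes a qualifying VTE a DLT carries no such limit, and neither does SAP 2.3. Enrolment resumed at 100 mg, a dose already studied (protocol 2.2.1.4), and SAP 5.1 has a single 100 mg group. One percentage could therefore mix participants assessed under different windows.

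**4. Wording behind the flags.** Protocol 4.1.3 counts qualifying VTEs whatever the investigator's view of causality, then says that an AE attributed to the underlying disease is not a DLT. The exemption in the evaluability and replacement wordings is toxicity in 4.1.1, DLT in 4.1.3, and drug-related toxicity in 7.4 and SAP 14.7.1. The first pair affects which VTEs are flagged. The evaluability wordings do not alter Table 3.22 today, but they matter once an evaluable set is built.

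**The case against.** The strongest reply is that the SAP does what the protocol asks. Protocol 9.6.2 assigns safety data to All-Treated, 9.6.2.2 asks only for DLTs by dose cohort, and the 75% rule sits among enrolment and replacement rules. Part 1 tests no hypothesis and the reporting is descriptive. This stands as far as it goes. A reader might infer that the SAP departs from a population the protocol prescribed for DLTs, and the documents do not support that. What remains is that neither document carries the protocol's own evaluability rule into the endpoint it governs. SAP section 8 leaves room to specify another population.

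On the window, SAP 2.3 itself calls a qualifying VTE within 8 (±1) weeks a DLT, so a 21-day table would contradict the SAP's own definition. The sponsor's standards may also define the term. Both points are fair and make the window issue smaller. Still, SAP 3.1 describes only 21 days, and nothing supplied ties the title to either window.

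A reader might also infer that late VTEs would vanish from the report. They would not: they still appear in Table 3.1 and Listing 14, and serious ones in Table 3.6. Listings 3, 9 and 11 (discontinuation, exposure, interruptions) would support a recount by evaluability. A reader should not have to rebuild a primary endpoint that way.

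**Conclusion.** The point holds as a reporting weakness in the primary endpoint. At any dose level with both a DLT and a DLT-free replaced participant, Table 3.22 shows a lower rate than the rate per evaluable participant. For one such participant the factor is between 0.750 and 0.923 over the protocol's range of 3 to 12 evaluable. These are illustrations on assumed counts. The actual effect is unknown, and it is zero if every treated participant was evaluable. On the window, the documents support only that VTE DLTs after Day 21 would be missing from Table 3.22 and Listing 22 if the period is read as 21 days. The 57% to 67% of window days should not be taken as a share of VTEs.

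It would be wrong to infer that dose decisions were affected. Table 3.22 is a final-analysis deliverable, while escalation rested on the N-CRM and the committee's data review.

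**What to change.** This is a cheap improvement.

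1. Add a DLT-Evaluable population to SAP section 4: All-Treated participants except those who received less than 75% of planned doses in the 21-day period for reasons other than toxicity, always keeping anyone who had a DLT. A set limited to those who reached 75% or had a DLT would be too narrow. It would drop DLT-free participants whose dosing fell short because of toxicity, whom the protocol keeps.
2. Present Table 3.22 on that population, with All Treated as supportive, and add an evaluability flag to Listing 22.
3. Define the Determinative Period as 21 days for general DLTs and the protocol's 8 (±1)-week window for qualifying VTEs. State the study day on which the program closes the latter.
4. Show VTE DLTs on a separate line that keeps every participant with a qualifying VTE in both numerator and denominator. Requiring completed follow-up alone could exclude someone who had a VTE and then left.
5. Present participants enrolled before and after Amendment 3 separately where the VTE window differs.
6. Before flags are programmed, reconcile the two protocol 4.1.3 sentences on VTE causality and disease-related AEs, and the evaluability wordings in protocol 4.1.1, 4.1.3, 7.4 and SAP 14.7.1.

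The cost is a little programming and SAP text. DLT percentages may look less favourable.

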## 14.10.6. Pharmacokinetic Tables

| Pharmacokinetic: Tables |            |                      |   |   |             |
|-------------------------|------------|----------------------|---|---|-------------|
| No.                     | Population | IDSL / Example Shell | Title   | Programming Notes   | Deliverable |
| PK                      |            |                      |   |   |             |
| 4.1                     | PK         | PK01                 | Summary of GSK3368715 Pharmacokinetic Concentration-Time Data by Dose Level, Cohort and Study Day | Use descriptive statistics (n, mean, SD, median, min and max) by planned relative assessment time; concentrations in ng/mL
Note: Separate 100mg dose by Dose Escalation, PK/PD and Combined (Dose Escalation and PK/PD) Cohorts. | SAC         |
| 4.2                     | PK         | PK01                 | Summary of GSK3963583 Pharmacokinetic Concentration-Time Data by Dose Level, Cohort and Study Day | Use descriptive statistics (n, mean, SD, median, min and max) by planned relative assessment time; concentrations in ng/mL
Note: Separate 100mg dose by Dose Escalation, PK/PD and Combined (Dose Escalation and PK/PD) Cohorts. | SAC         |
| 4.3                     | PK         | PK01                 | Summary of GSK3983164 Pharmacokinetic Concentration-Time Data by Dose Level, Cohort and Study Day | Use descriptive statistics (n, mean, SD, median, min and max) by planned relative assessment time; concentrations in ng/mL
Note: Separate 100mg dose by Dose Escalation, PK/PD and Combined (Dose Escalation and PK/PD) Cohorts. | SAC         |

| Pharmacokinetic: Tables |            |                      |  |  |             |
|-------------------------|------------|----------------------|--|--|-------------|
| No.                     | Population | IDSL / Example Shell | Title  | Programming Notes  | Deliverable |
| 4.4                     | PK         | PK06                 | Summary of Derived GSK3368715 Pharmacokinetic Parameters by Dose Level, Cohort and Study Day | 
PK parameters: Cmax, Tmax, Ctrough, AUC0-t, AUC0-tau, AUCinf, t1/2, λz, TI and AR determined from the concentration-time data in ng/ml;
descriptive summaries: mean, SD, median, min, max, geometric mean & SD, CV%, and 95%CI of log-transformed parameters, if applicable.
 
Note: Separate 100mg dose by Dose Escalation, PK/PD and Combined (Dose Escalation and PK/PD) Cohorts.
                  | SAC         |
| 4.5                     | PK         | PK06                 | Summary of Derived GSK3963583 Pharmacokinetic Parameters by Dose Level, Cohort and Study Day | 
PK parameters: Cmax, Tmax, Ctrough, AUC0-t, AUC0-tau, AUCinf, t1/2, λz, TI, AR, RCMAXM1 and RAUCM1 determined from the concentration-time data in ng/ml;
descriptive summaries: mean, SD, median, min, max, geometric mean & SD, CV%, and 95%CI of log-transformed parameters, if applicable.
 
Note: Separate 100mg dose by Dose Escalation, PK/PD and Combined (Dose Escalation and PK/PD) Cohorts.
 | SAC         |

| Pharmacokinetic: Tables |            |                      |  |   |             |
|-------------------------|------------|----------------------|--|---|-------------|
| No.                     | Population | IDSL / Example Shell | Title  | Programming Notes   | Deliverable |
| 4.6                     | PK         | PK06                 | Summary of Derived GSK3983164 Pharmacokinetic Parameters by Dose Level, Cohort and Study Day | PK parameters: Cmax, Tmax, Ctrough, AUC0-t, AUC0-tau, AUCinf, t 1/2 , λz, Tl, AR, RCMAXM2 and RAUCM2 determined from the concentration-time data in ng/ml; descriptive summaries: mean, SD, median, min, max, geometric mean & SD, CV%, and 95%CI of log-transformed parameters, if applicable.
Note: Separate 100mg dose by Dose Escalation, PK/PD and Combined (Dose Escalation and PK/PD) Cohorts. | SAC         |
| 4.10                    | PK         |                      | Summary Results of Single Dose Proportionality Assessment Using Power Model for GSK3368715   |   | SAC         |

## 14.10.7. Pharmacokinetic Figures

| Pharmacokinetic: Figures |            |                      |  |   |             |
|--------------------------|------------|----------------------|--|---|-------------|
| No.                      | Population | IDSL / Example Shell | Title  | Programming Notes   | Deliverable |
| PK                |            |                      |  |   |             |
| 4.11                     | PK         | PK16                 | Individual GSK3368715 Concentration-Time Plots (Linear and Semi-Log) by Dose Level, Cohort and Study Day | ng/mL   | SAC         |
| 4.12                     | PK         | PK16                 | Individual GSK3963583 Concentration-Time Plots (Linear and Semi-Log) by Dose Level, Cohort and Study Day | ng/mL   | SAC         |
| 4.13                     | PK         | PK16                 | Individual GSK3983164 Concentration-Time Plots (Linear and Semi-Log) by Dose Level, Cohort and Study Day | ng/mL   | SAC         |
| 4.14                     | PK         | PK17                 | Mean Concentration-Time Plots (Linear and Semi-Log) by Dose Level, Cohort and Study Day                  | GSK3368715 and metabolites (GSK3963583 and GSK3983164) concentration time profiles will be overlaid on the same plot once concentrations have been converted to nM concentrations.
Note: Separate 100mg dose by Dose Escalation, PK/PD and Combined (Dose Escalation and PK/PD) Cohorts. | SAC         |
| 4.15                     | PK         | PK18                 | Median Concentration-Time Plots (Linear and Semi-Log) by Dose Level, Cohort and Study Day                | GSK3368715 and metabolites (GSK3963583 and GSK3983164) concentration time profiles will be overlaid on the same plot once concentrations have been converted to nM concentrations.
Note: Separate 100mg dose by Dose Escalation, PK/PD and Combined (Dose Escalation and PK/PD) Cohorts. | SAC         |

## 14.10.8. ICH Listings

| ICH: Listings                                   |             |                      |  |   |             |
|---|-------------|----------------------|--|---|-------------|
| No.   | Population  | IDSL / Example Shell | Title  | Programming Notes   | Deliverable |
| Subject Disposition                      |             |                      |  |   |             |
| 1.  | Screened    | ES7                  | Listing of Reasons for Screen Failure                                | Journal Guidelines  | SAC         |
| 2.  | All Treated | ES2                  | Listing of Reasons for Study Withdrawal                              | ICH E3  | SAC         |
| 3.  | All Treated | SD2                  | Listing of Reasons for Study Treatment Discontinuation               | ICH E3  | SAC         |
| Protocol Deviations                      |             |                      |  |   |             |
| 4.  | All Treated | DV2                  | Listing of Protocol Deviations                                       | ICH E3
Report all PDs  | SAC         |
| 5.  | All Treated | IE3                  | Listing of Participants with Inclusion/Exclusion Criteria Deviations | ICH E3  | SAC         |
| Demographic and Baseline Characteristics |             |                      |  |   |             |
| 6.  | All Treated | DM2                  | Listing of Demographic Characteristics                               | ICH E3  | SAC         |
| 7.  | All Treated | DM9                  | Listing of Race  | ICH E3  | SAC         |
| Prior and Concomitant Medications        |             |                      |  |   |             |
| 8.  | All Treated | CP_CM3               | Listing of Concomitant Medications                                   | IDSL
Note: IDSL shell in development. Required for ClinPharm studies instead of a corresponding table. Not required for studies where a table is produced. | SAC         |
| Exposure                                 |             |                      |  |   |             |
| 9.  | All Treated | OEX3A                | Listing of Treatment Exposure to GSK3368715                          | ICH E3  | DE, SAC     |
| Dose Modifications                       |             |                      |  |   |             |
| 10.   | All Treated | ODMOD10A             | Listing of Dose Reductions   | ICH E3  | SAC         |

**CONFIDENTIAL**

207675

| ICH: Listings                                |                   |                             |   |                          |                    |
|---|-------------------|-----------------------------|---|--------------------------|--------------------|
| No.  | Population | IDSL / Example Shell | Title  | Programming Notes | Deliverable |
| 11.   | All Treated       | ODMOD11A                    | Listing of Dose Interruptions   | ICH E3                   | SAC                |
| Response                                     |                   |                             |   |                          |                    |
| 12.   | All Treated       | RE5                         | Listing of Responses without Confirmation (RECIST 1.1 Criteria)                   |                          | SAC                |
| 13.   | All Treated,      | RE12                        | Listing of Subject Best Response  |                          | SAC                |
| Adverse Events                               |                   |                             |   |                          |                    |
| 14.   | All Treated       | AE8                         | Listing of All Adverse Events   | ICH E3                   | DE, SAC            |
| 15.   | All Treated       | AE7                         | Listing of Subject Numbers for Individual Adverse Events                          | ICH E3                   | SAC                |
| Serious and Other Significant Adverse Events |                   |                             |   |                          |                    |
| 16.   | All Treated       | AE8                         | Listing of Fatal Serious Adverse Events   | ICH E3                   | SAC                |
| 17.   | All Treated       | AE8                         | Listing of Non-Fatal Serious Adverse Events                                       | ICH E3                   | SAC                |
| 18.   | All Treated       | AE14                        | Listing of Reasons for Considering as a Serious Adverse Event                     | ICH E3                   | SAC                |
| 19.   | All Treated       | AE8                         | Listing of Adverse Events Leading to Permanent Discontinuation of Study Treatment | ICH E3                   | SAC                |
| 20.   | All Treated       | AE8                         | Listing of Adverse Events Leading to Dose Interruptions of Study Treatment        | ICH E3                   | SAC                |
| 21.   | All Treated       | AE8                         | Listing of Adverse Events Leading to Dose reductions of Study Treatment           | ICH E3                   | SAC                |
| Dose-Limiting Toxicities                     |                   |                             |   |                          |                    |
| 22.   | All Treated       | DL3                         | Listing of Dose-Limiting Toxicities (DLT) During the Determinative Period         |                          | SAC                |

